10.2.8.4 Management of Specific AEs

10.2.8.4.1 Sinus Tachycardia

CTCAE Grade	Management
CTCAE v5.0 Grade 2 sinus tachycardia (ie, Symptomatic ^a ; nonurgent medical intervention indicated) with HR 120 and above at rest for at least 5 minutes with no physical exertion.	Evaluate ECG for abnormalities, manage as per local guidelines and call the medical monitor immediately.
Any CTCAE v5.0 Grade 3 sinus tachycardia (ie, urgent medical intervention indicated) or Grade 4 (life-threatening)	Evaluate ECG for abnormalities, manage as per local guidelines and call the medical monitor immediately. In all subjects, discontinue further treatment with study drug.

CTCAE: Common Terminology Criteria for Adverse Events; ECG: electrocardiogram.

^a Symptoms may include dizziness, light headedness, chest pain, chest heaviness, palpitations, and shortness of breath.

If a subject complains of palpitations, dizziness, breathlessness, chest tightness, or any other symptoms suggestive of arrhythmia, the subject should be advised to lie flat, and pulse and BP should be measured and recorded, followed by a 12-lead ECG (urgently if hypotension is detected; otherwise as soon as is feasible). The BP, pulse, and ECG measurements will be reviewed by the investigator, who will use their clinical judgment regarding further monitoring and management.

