6.2 Stopping Rules

6.2.1 Stopping Criteria for Individual Subjects

Subjects will permanently discontinue study drug for any study drug-related adverse events that are rated Grade ≥ 3 in severity on the National Cancer Institute (NCI) Common Terminology Criteria for Adverse Events (CTCAE) scale (v5.0).

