6.2.2 Criteria for Premature Termination or Suspension of the Study

The study will be completed as planned unless one or more of the following criteria are satisfied that require temporary suspension or early termination of the study:

- Any subject experiences a Hy's Law reaction (defined as alanine aminotransferase [ALT] or aspartate aminotransferase [AST] $>3 \times$ the upper limit of normal [ULN] in conjunction with elevated total bilirubin $>2 \times$ ULN without findings of cholestasis or other alternate etiology).
- New information or other evaluation regarding the safety or efficacy of the study drug that indicates a change in the known risk profile for TAK-510, such that the risk is no longer acceptable for subjects participating in the study.
- Significant violation of Good Clinical Practice (GCP) that compromises the ability to achieve the primary study objectives or compromises subject safety.
- The sponsor elects to terminate or suspend the study for administrative reasons including plans to modify, suspend, or discontinue development of the study drug.

In addition, the study may be interrupted for review of the safety data during Parts 1, 2, or 3 if one of the below criteria is met:

- Two or more subjects experience a sinus tachycardia with HR >120 bpm at rest while semirecumbent with symptoms of palpitation or lightheadedness requiring medical intervention and considered related to TAK-510, or
- Two or more subjects experience a CTCAE v5.0 Grade ≥ 3 hypotension (ie, requiring medical intervention) and considered related to TAK-510, or
- One subject experiences a CTCAE v5.0 Grade ≥ 3 syncope (fainting or orthostatic collapse) and considered related to TAK-510, or

- Two or more subjects experience a CTCAE v5.0 Grade 3 event considered related to TAK-510 administration, or
- One subject experience a CTCAE v5.0 Grade 4 event considered related to TAK-510 administration, or
- One subject with ALT or AST $>5 \times$ ULN after TAK-510 administration, or
- One subject with ALT or AST $>3 \times$ ULN with appearance of fatigue, nausea, vomiting, right upper quadrant pain or tenderness, fever, rash, and/or eosinophilia ($>5\%$), or
- One subject with increases in creatinine $>1.5 \times$ ULN after TAK-510 administration, or
- One subject with a serious adverse event (SAE) considered related to TAK-510 administration, or

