10.2.8.4.2 Low BP

If a subject develops symptoms suggestive of hypotension or postural hypotension, BP should be assessed for evidence of hypotension, which should be managed as per local guidelines, and the medical monitor should be contacted. TAK-510 administration will be discontinued on occurrence of an event of CTCAE v5.0 Grade ≥ 3 hypotension (ie, requiring medical intervention).

If systolic BP is <85 mm Hg or if the subject is experiencing symptoms suggestive of postural hypotension after standing, the subject should be advised to lie flat, and BP and HR should be rechecked in that position. If systolic BP remains <85 mm Hg, a 12-lead ECG should be performed and the investigator will use their clinical judgment regarding further monitoring and management.

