10.2.8.4.3 Injection Site Reaction

If a subject develops a CTCAE v5.0 Grade 3 (ulceration or necrosis; severe tissue damage; need for operative intervention) or Grade 4 (life-threatening consequences; urgent intervention indicated), discontinue administration of TAK-510, provide immediate treatment, and contact the medical monitor. Any injection site reaction assessed as a CTCAE v5.0 Grade 2 (ie, pain, lipodystrophy, edema, phlebitis) should be managed according to standard of care. Symptomatic treatment should be administered, and the investigator should contact the medical monitor.

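### For Grade 3 or higher tachycardia, hypotension and injection site reaction, Section 6.2.1 ties individual discontinuation to relatedness and Section 10.2.8.4 does not; the scope of the all-subjects phrase for tachycardia is undefined

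*Protocol*

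**What the plan says.** **Individual stopping rule (Protocol 6.2.1).** "Subjects will permanently discontinue study drug for any study drug-related adverse events" of Grade 3 or higher on CTCAE v5.0. The rule concerns the individual subject and is conditioned on relatedness.

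**Event-specific management (Protocol 10.2.8.4).**
- Sinus tachycardia (10.2.8.4.1): the trigger is "Any CTCAE v5.0 Grade 3 sinus tachycardia (ie, urgent medical intervention indicated) or Grade 4 (life-threatening", closing the bracket. The action is "In all subjects, discontinue further treatment with study drug". No causality condition is given.
- Low BP (10.2.8.4.2): "TAK-510 administration will be discontinued on occurrence of an event of CTCAE v5.0 Grade" 3 or higher hypotension. No causality condition is given.
- Injection site reaction (10.2.8.4.3): if a subject has a Grade 3 or 4 reaction, "discontinue administration of TAK-510, provide immediate treatment, and contact the medical monitor". No causality condition is given.

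**Study-level rule (Protocol 6.2.2).** Effects beyond the affected subject are handled here. A list of triggers allows, but does not require, an interruption for safety review. One of them is "Two or more subjects experience a CTCAE v5.0 Grade 3 event considered related to TAK-510 administration". Others need a single subject, for example a related Grade 4 event, a related SAE or a related Grade 3 or higher syncope.

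Section 10.1.2 names injection site reactions, hypotension and tachycardia as the adverse events of special interest.

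**The concern.** The section headed as the stopping rule for individual subjects and the section that site staff would open when the event happens do not state the same condition. For a Grade 3 or higher event of these three kinds that the investigator judges not related, 6.2.1 by itself does not require the subject to stop, whereas 10.2.8.4 does. The document has no precedence clause. Section 7.5 does not settle the matter, because its adverse event category uses another standard (unacceptable risk, or the subject's unwillingness to go on).

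The tachycardia row has a second problem. Its all-subjects phrase is not defined, and the two neighbouring subsections contain nothing like it.

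At stake is who receives the remaining daily doses in Parts 2 and 3 and the Day 14 redose in Part 3. Repeat-dose tolerability is the primary objective of those parts, and tolerability of the redose is a secondary objective of Part 3. Section 1.0 allows up to 2 sites, so the rule could be applied in two ways within one study.

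**Working it through.** The documents state no number of subjects stopped per event. The check is therefore a side-by-side reading, plus simple counts.

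**1. Cohort size (Sections 1.0 and 6.1).** Each cohort has 8 subjects randomized 3:1, that is 6 on TAK-510 and 2 on placebo. The stated totals reproduce: 17 × 8 = 136 (Part 1), 8 × 8 = 64 (Part 2), 3 × 8 = 24 (Part 3).

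**2. Where the rule can act.** Part 1 gives a single dose, so an already dosed subject has nothing left to discontinue. The issue is confined to Parts 2 and 3: 8 + 3 = 11 cohorts and up to 64 + 24 = 88 of 136 + 64 + 24 = 224 planned subjects.

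**3. The rules side by side, for one Grade 3 event of these types in one subject.** Sections 10.2.8.4.2 and 10.2.8.4.3 speak of TAK-510. I read this as blinded study drug, because Section 8.1.3 blinds the investigator.

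| Investigator's judgment | Required to stop under 6.2.1 alone | Required to stop under 10.2.8.4 (affected subject) |
|---|---|---|
| Related | 1 | 1 |
| Not related | 0 | 1 |

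The sections differ only in the second row, by one subject per event.

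**4. Doses that depend on it.**
- Part 2 has daily dosing on Days 1 to 5. An event after the Day 1 dose leaves 5 − 1 = 4 doses.
- Part 3 has Days 1 to 7 plus Day 14. An event after the Day 1 dose leaves (7 − 1) + 1 = 7 doses.
- These are maxima. Later events leave fewer, and after the last dose none.
- One subject is 1 of 6 in the active group of a cohort, or 1 of 2 in the placebo group.

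**5. Is the causality condition deliberate elsewhere?** Largely yes. In 6.2.2 the triggers for tachycardia, hypotension, syncope, Grade 3 events, Grade 4 events and SAEs all require relatedness. The liver, creatinine and injection site triggers there do not. The Amendment 3 summary (Section 1.1, change 17) records that relatedness wording was added in 6.2.2 for consistency. Change 28 edited 10.2.8.4.3 in the same amendment. The current 10.2.8.4.1 to 10.2.8.4.3 neither carry a matching condition nor say that they apply whatever the cause.

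**6. Scope of the tachycardia instruction.** The phrase stands in the management cell of a row about one grade of one event, under a heading on managing specific adverse events. The neighbouring subsections are written around a single subject. Every subject who has the event is the natural meaning, but the text does not say so.

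**The case against.** The strongest reply is that these are a general rule and a set of specific rules. Section 6.2.1 gives a condition under which a subject must stop; it does not say that this is the only one. Section 7.5 already allows discontinuation on grounds other than relatedness, and 10.2.8.4.4 treats hypersensitivity in the same event-specific way. A site that stops the affected subject obeys everything. In addition, Section 10.2.2 defines related broadly, so few postdose events of these types are likely to be called not related. The study is also descriptive, with no test to distort. All of this stands, and it limits the finding to an inconsistency of wording. It does not remove it: a reader who opens 6.2.1 alone reaches another answer than one who opens 10.2.8.4.

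Three stronger readings are tempting, and the documents do not support them.
- *One Grade 3 tachycardia stops all 8 subjects of a cohort.* A reader might infer this from the all-subjects phrase taken literally. The text never mentions the cohort. On that reading a single event would end dosing for everyone, whereas 6.2.2 has its own triggers and then only permits an interruption.
- *Section 6.2.2 needs a second related Grade 3 event before an interruption is considered.* That holds for one trigger. Others need one subject, and a Grade 3 tachycardia calling for urgent intervention might itself qualify as an SAE under 10.1.1.
- *A stop without a causality condition selectively removes placebo subjects.* Section 6.2.1 applies to study drug, which 9.2.7 defines as TAK-510 or placebo, and relatedness is judged blind. A placebo subject whose event is judged related stops under 6.2.1 as well.

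**Conclusion.** The point holds in a limited form and should be corrected. For Grade 3 or higher sinus tachycardia, hypotension and injection site reaction, 6.2.1 makes discontinuation depend on relatedness and 10.2.8.4.1 to 10.2.8.4.3 do not. The size is 0 against 1 subject required to stop, for each event judged not related, in Parts 2 and 3 only. Other Grade 3 events that 10.2.8.4 does not name fall under 6.2.1 without this conflict.

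This rests on two readings: that 6.2.1 is taken by itself, and that the all-subjects phrase means those who have the event. How often such an event would be judged not related cannot be estimated from the protocol, which gives no event rates. The reason to act is that the wording governs an operative stopping rule for the study's named safety signals, not that a large effect on the summaries has been shown.

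**What to change.** Reconcile 6.2.1 with 10.2.8.4.1, 10.2.8.4.2 and 10.2.8.4.3:
- State once whether causality matters for these three events, and name whose dosing stops.
- In 10.2.8.4.1, replace the all-subjects phrase with wording of defined scope that is consistent with 6.2.2.
- Cross-refer between the individual stopping rule, the management subsections and 6.2.2, so that each points to the same rule.

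Which rule is right is a decision for the sponsor's clinical team. The cost is protocol wording in four subsections, with no new procedures, visits or data.

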10.2.8.4.2 Low BP

If a subject develops symptoms suggestive of hypotension or postural hypotension, BP should be assessed for evidence of hypotension, which should be managed as per local guidelines, and the medical monitor should be contacted. TAK-510 administration will be discontinued on occurrence of an event of CTCAE v5.0 Grade ≥ 3 hypotension (ie, requiring medical intervention).

If systolic BP is <85 mm Hg or if the subject is experiencing symptoms suggestive of postural hypotension after standing, the subject should be advised to lie flat, and BP and HR should be rechecked in that position. If systolic BP remains <85 mm Hg, a 12-lead ECG should be performed and the investigator will use their clinical judgment regarding further monitoring and management.

10.2.8.4.3 Injection Site Reaction

If a subject develops a CTCAE v5.0 Grade 3 (ulceration or necrosis; severe tissue damage; need for operative intervention) or Grade 4 (life-threatening consequences; urgent intervention indicated), discontinue administration of TAK-510, provide immediate treatment, and contact the medical monitor. Any injection site reaction assessed as a CTCAE v5.0 Grade 2 (ie, pain, lipodystrophy, edema, phlebitis) should be managed according to standard of care. Symptomatic treatment should be administered, and the investigator should contact the medical monitor.

10.2.8.4.4 Hypersensitivity

If anaphylaxis or other serious allergic reactions occur, TAK-510 administration will be discontinued immediately and appropriate management initiated (eg, epinephrine, antihistamines, and further immediate care as necessary).

10.2.8.5 Reporting of Abnormal LFTs

If a subject is noted to have ALT or AST $>3 \times$ ULN and total bilirubin $>2 \times$ ULN, the event should be recorded as an SAE and reported as per Section 10.2.8.3. The investigator must contact the medical monitor for discussion of the relevant subject details and possible alternative etiologies, such as acute viral hepatitis A or B or other acute liver disease. Follow-up laboratory tests as described in Section 9.2.9 must also be performed.

10.2.9 Safety Reporting to Investigators, IRBs and/or IECs, and Regulatory Authorities

The sponsor will be responsible for reporting all suspected unexpected serious adverse reactions (SUSARs) and any other applicable SAEs to regulatory authorities, investigators and IRBs and/or IECs, as applicable, in accordance with national regulations in the countries where the study is conducted. Relative to the first awareness of the event by or further provision to the sponsor or sponsor's designee, SUSARs will be submitted within 7 days for fatal and life-threatening events and 15 days for other serious events, unless otherwise required by national regulations. The sponsor will also prepare an expedited report for other safety issues where these might materially alter the current benefit-risk assessment of an investigational medicinal product or that would be sufficient to consider changes in the investigational medicinal products administration or in the overall conduct of the study. The investigational site also will forward a copy of all expedited reports to his or her IRB and/or IEC in accordance with national regulations.

11.0 STATISTICAL METHODS

11.1 Statistical and Analytical Plans

A statistical analysis plan will be prepared and finalized before database lock. This document will provide further details regarding the definition of analysis variables and analysis methodology to address all study objectives.

A targeted data review will be conducted before database lock. This review will assess the accuracy and completeness of the study database, subject evaluability, or appropriateness of the planned statistical methods.

The impact due to COVID-19 will be summarized and listed based on all randomized subjects, where appropriate.

11.1.1 Analysis Sets

11.1.1.1 Safety Analysis Set

The safety analysis set consists of all subjects who are randomized and receive at least 1 dose of study treatment. Subjects will be analyzed according to the study treatment actually received.

11.1.1.2 PK Analysis Set

The PK analysis set consists of all subjects who receive at least 1 dose of TAK-510 and have at least 1 measurable postdose plasma or urine concentration for TAK-510.

11.1.1.3 Immunogenicity Analysis Set

The immunogenicity analysis set consists of all subjects who receive at least 1 dose of study treatment and have the baseline sample and at least 1 postbaseline sample ADA assessment.

11.1.2 Analysis of Demography and Other Baseline Characteristics

Descriptive statistics (n, mean, standard deviation, median, minimum, and maximum) will be provided for continuous demographic variables and baseline characteristics variables (eg, age, height, weight, and BMI) for placebo, each TAK-510 dose level (Parts 1 and 2)/dose regimen (Part 3), and TAK-510 overall in Parts 1, 2, and 3 separately. The number and percentage of subjects in each class of the categorical demographic variables and baseline characteristics variables (eg, gender, ethnicity, race) will be tabulated for placebo, each TAK-510 dose level (Parts 1 and 2)/dose regimen (Part 3), and TAK-510 overall in Parts 1, 2, and 3 separately. Placebo data will be pooled across cohorts within each part of the study. The same dose level (Parts 1 and 2)/dose regimen (Part 3) will be pooled across cohorts within each part of the study where appropriate. The safety analysis set will be used to summarize the demographics and baseline characteristics. All data will be provided in by-subject listings.

11.1.3 PK Analysis

The plasma (all parts of the study) and urine (Parts 1 and 2 only) concentrations of TAK-510 will be summarized by dose level (Parts 1 and 2 only)/dose regimen (Part 3 only) at each scheduled sampling day/time within each part of the study separately, using descriptive statistics (n, mean, standard deviation, geometric mean, percent coefficient of variation [%CV], median, minimum, and maximum) based on the PK analysis set. The PK parameters of TAK-510 determined using a noncompartmental analysis approach will be summarized by dose level (Parts 1 and 2 only)/dose regimen (Part 3 only) of TAK-510, as appropriate, within each part of the study separately, using descriptive statistics (n, mean, standard deviation, geometric mean, %CV, median, minimum, and maximum) based on the PK analysis set. Dose proportionality may be assessed graphically (log-transformed dose-normalized C_{max} and AUC versus dose) and by using a power model within each part of the study separately as data allow; no formal statistical comparisons will be conducted. The same dose level (Parts 1 and 2 only)/dose regimen (Part 3 only) may be pooled across cohorts within each part of the study where appropriate. All data will be provided in by subject listings.

A population PK analysis may be conducted and a more detailed description of these analyses will be given in a separate analysis plan. The results from these analyses will not be included in the CSR and may be a standalone report.

11.1.4 Safety Analysis

Safety analyses will be based on the safety analysis set. No formal statistical tests or inference will be performed for safety analyses. All safety summary analyses will be performed by placebo, TAK-510 dose level (Parts 1 and 2 only)/dose regimen (Part 3 only), and TAK-510 overall within each part of the study separately. In particular, the number and percentage of subjects with at least 1 postdose value meeting the sponsor's markedly abnormal criteria for BP and HR will be provided. Placebo data will be pooled across cohorts within each part of the study. The same dose level (Parts 1 and 2 only)/dose regimen (Part 3 only) will be pooled across cohorts within each part of the study where appropriate. For Part 3 only, similar safety summary analyses (excluding ADA assessments) will be performed for the single dose after washout from multiple dose regimens of TAK-510 by placebo, TAK-510 single dose level after washout, and TAK-510 single dose overall after washout. All data will be provided in by subject listings.

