LFTs							X		X									
Serum sample for CK ^j				X	X							X					X	
Glucose finger stick ^k				X	X	X	X	X	X	X	X				X			
Urine drug screen	X	X													X			
Alcohol breath test		X													X			
Cotinine test	X	X													X			
Hepatitis screen ^l	X																	
HIV test	X																	
βhCG (pregnancy) test ^m	X	X										X		X			X	
Serum FSH test ⁿ	X																	
PK Evaluations																		
Plasma sample for TAK-510 PK				X	X	X	X	X	X	X	X				X	X	X	
Immunogenicity and Biomarkers																		
Serum sample for immunogenicity ^o				X								X			X		X	

CONFIDENTIAL

Table 3.f Part 3 for Dose Titration and Redosing Cohorts 18 to 20: Screening Through Day 15, Follow-Up, and ET

	Days															ET		
	Screen	-28 to -3	-2 ^a	-1	Dosing							8 (Discharge)	9 to 13 Wash out ^b	Day 13 ±1 day (Confine again)	Day 14 ±1 day (Single Dose)	Day 15 ±1 day (Discharge)	Follow-up Visit Day 29 ±3 days	
					Pre dose	1	2	3	4	5	6							
Blood sample for DNA (optional) ^p												X					X	
Other																		
Confinement ^s			X-----									X		X-----X				

ADA: antidrug antibodies; AE: adverse event; anti-HCV: antibodies to hepatitis C virus; β hCG: beta human chorionic gonadotropin; BMI: body mass index; BP: blood pressure; CK: creatine kinase; ECG: electrocardiogram; ET: early termination; FSH: follicle-stimulating hormone; [REDACTED]; HBsAg: hepatitis B surface antigen; LFT: liver function test; PK: pharmacokinetic.

^a Subjects will be admitted to the site on Day -2.

^b Based on emerging safety, tolerability, and available PK data, subjects may be confined during washout at the discretion of the investigator in consultation with the sponsor and medical monitor. Duration of washout period may be shortened or lengthened in Cohorts 19 and 20 based on emerging data, refer to Section 6.1.4 for confinement and discharge during redosing interval.

^c Physical examination at the indicated visit will be symptom-driven.

^d Vital signs will include body temperature, BP, respiratory rate, and pulse. On Day -1 and on dosing days, vital signs will be collected as described in Table 3.g (Part 3 Screening Through Day 1 Assessments), Table 3.h (Part 3 Days 2 to 6 Assessments), Table 3.i (Part 3 Day 7 and Day 8 Assessments), and Table 3.j (Part 3 Day 9 Through Day 15 Assessments, Follow-Up, and ET).

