Optional DNA samples will also be collected from subjects that provide consent for collection through a separate procedure. DNA samples can be collected at any time on the day of discharge (Day 8) or at early termination (if applicable). Subjects will be discharged on Day 8 and will be readmitted the evening prior to redosing. After a 7-day washout (168 hours after the last dose of the 7-day treatment period), subjects will be dosed with a single dose of study drug (ie, at the same dose and double-blind treatment assignment as their highest daily dose during the 7-day treatment period). The duration of washout may be subject to change based on emerging safety, tolerability, and available PK data. Subjects will be confined the evening prior to redosing and for at least 30 hours after their redosing, while not being confined for the entire washout period. Subjects will return after discharge for additional immunogenicity and other assessments at follow-up visits on Day 29. Based on emerging safety, tolerability, and available PK data, subjects may be confined during washout at the discretion of the investigator in consultation with the sponsor and medical monitor.

In Part 3, up to 3 cohorts may be dosed sequentially for 7 days using a dose titration design of 1 to 5 days at lower doses followed by 2 to 6 days at the highest dose for that cohort, which will not exceed the dose studied in the highest completed dose cohort in Part 2. Cohorts 18 and 19 may be started in parallel. The proposed dose titration designs for the 3 cohorts are as follows:

Cohort 18: Single doses that escalate on a daily basis will be given on the first 2 to 5 days of the 7-day dosing period, followed by a maximum daily dose on the remaining days of the 7-day dosing period.

Cohort 19: A lower starting dose will be given on the first 2 to 3 days of the 7-day dosing period, followed by a maximum daily dose for the remaining days of the 7-day dosing period. The lower starting dose is to be determined based on Cohort 18.

Cohort 20: The initial daily dose(s) are to be determined by Cohorts 18 and 19 and will be given on the first 1 to 3 days, followed by the maximum daily dose for the remaining days of the 7-day dosing period. The maximum daily dose will be the same as that Cohorts 18 and 19, or higher as supported by safety, tolerability, and PK data from at least the same daily dose (or higher) in Part 2 MRD cohorts.

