6.3.2.5 Rationale for Dose Titration and Redosing After Washout

Part 3 of the study is intended to evaluate whether dose titration can result in a different tolerability, particularly with regard to cardiovascular effects, and whether redosing after a 7-day washout results in cardiovascular effects (ie, loss of potential attenuation of cardiovascular effects with dose titration and multiple dosing). GLP-compliant and non-GLP-compliant cardiovascular safety studies in telemetered dogs with TAK-510 have demonstrated: (1) a dose-response of cardiovascular effects, where the lowest dose tested [REDACTED] results in an ~ED₅₀ (median effective dose) of maximal heart rate and blood pressure effects observed in dogs; (2) repeat-dosing at therapeutic doses results in a significant attenuation of cardiovascular effects following administration of the second daily dose. These data demonstrate that sub-therapeutic

doses can elicit minimal cardiovascular effects and that repeat dosing may elicit tachyphylaxis. Thus, Part 3 of this study is designed to test these concepts clinically to identify the appropriate tolerizing doses, escalation, and length of time of exposure that can potentially minimize cardiovascular effects at therapeutic doses.

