11.1.4.1 AEs

The summary of treatment-emergent adverse events (TEAEs) will include the number and percentage of subjects with at least 1 TEAE by MedDRA System Organ Class and Preferred Term and by placebo, each TAK-510 dose level (Parts 1 and 2 only)/dose regimen (Part 3), and TAK-510 overall within each part of the study separately. Similar summary analyses will be provided for treatment-related TEAEs, SAEs, AESIs, and AEs leading to permanent treatment discontinuation as well. For Part 3 only, similar summary analyses of TEAEs will be performed for the single dose after 7 days of washout from multiple dose regimens of TAK-510 by placebo, TAK-510 single dose level after washout, and TAK-510 single dose overall after washout.

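### The Part 3 rechallenge safety tables are grouped by single dose level and overall, with no dose-regimen level, so cohorts with different titration schedules can be merged and cannot be lined up with the by-regimen tables

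*Protocol*

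**What the plan says.** Section 11.1.4 of the protocol sets the general rule: "All safety summary analyses will be performed by placebo, TAK-510 dose level (Parts 1 and 2 only)/dose regimen (Part 3 only), and TAK-510 overall". For the single dose after washout in Part 3 it then fixes a different grouping: "by placebo, TAK-510 single dose level after washout, and TAK-510 single dose overall after washout". Section 1.0 gives the same grouping, and Sections 11.1.4.1 to 11.1.4.4 repeat it for adverse events, laboratory data, vital signs and ECG. No regimen, cohort or washout level is named.

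Section 6.1.4 sets the redose "at the same dose and double-blind treatment assignment as their highest daily dose during the 7-day treatment period". It describes three titration schedules, one per cohort, and says of Cohort 20: "The maximum daily dose will be the same as that Cohorts 18 and 19, or higher as supported by safety, tolerability, and PK data". On washout, Table 3.f footnote b states: "Duration of washout period may be shortened or lengthened in Cohorts 19 and 20 based on emerging data". Table 3.j footnote a says the same, and Section 6.1.4 allows the duration to change without naming cohorts. Sections 11.1.4.1 to 11.1.4.4 nevertheless introduce the rechallenge summaries as being "for the single dose after 7 days of washout from multiple dose regimens of TAK-510".

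Section 6.3.2.5 gives the purpose of the redosing: to see "whether redosing after a 7-day washout results in cardiovascular effects (ie, loss of potential attenuation of cardiovascular effects with dose titration and multiple dosing". The same section says Part 3 is meant to find suitable tolerizing doses, escalation and duration of exposure.

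**The concern.** Loss of attenuation is a within-regimen question: how did subjects on a given titration respond before the washout, and how do the same subjects respond after it? The pre-washout tables answer the first half by regimen. The rechallenge tables answer the second half by dose, which the cohorts may have in common, and leave out the titration schedule, which is what distinguishes the cohorts by design.

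At stake is a stated secondary objective of Part 3, the safety and tolerability of the rechallenge dose. If cohorts share a maximum dose, a regimen whose subjects react again on Day 14 and one whose subjects do not would be averaged, and the summary would describe neither. Sections 11.1.4.1 to 11.1.4.4 also tie these summaries to a 7-day interval that the protocol elsewhere allows to change.

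**Working it through.** **Inputs, all from the protocol.** Part 3 has up to 3 cohorts of 8 subjects, randomised 3:1, so 6 TAK-510 and 2 placebo each (Section 6.1.4, Table 6.a). Stated total: about 24. There is no hypothesis test or power calculation (Section 11.3).

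**Reproducing the stated figure.** 3 × 8 = 24, which agrees. Active: 3 × 6 = 18. Placebo: 3 × 2 = 6.

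**What differs between cohorts at one shared dose.** Days at the maximum dose = 7 − days of titration (Section 6.1.4):

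| Cohort | Titration | Titration days | Days at maximum |
|---|---|---|---|
| 18 | escalating daily | 2–5 | 2–5 |
| 19 | one lower starting dose | 2–3 | 4–5 |
| 20 | initial dose(s) set from 18 and 19 | 1–3 | 4–6 |

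**What the planned grouping does.** The redose equals the subject's own maximum, so cohorts with the same maximum have the same single dose level.

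- Two cohorts share a maximum (for example 18 and 19, which the Cohort 20 text treats as having a common one): one column of 2 × 6 = 12 active subjects.
- All three share it: one column of 3 × 6 = 18, identical to the overall column.
- By regimen: up to three columns of 6.

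**Size of the masking, with assumed counts.** Suppose 3 of 6 subjects in one cohort have a markedly abnormal BP or HR value at rechallenge and nobody in the other cohorts does. These counts are not in the protocol. Exact (Clopper-Pearson) 95% intervals:

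| Presentation | Result | 95% interval |
|---|---|---|
| By regimen, affected cohort | 3/6 = 50% | 11.8% to 88.2% |
| By regimen, each other cohort | 0/6 = 0% | 0% to 45.9% |
| By dose level, two cohorts merged | 3/12 = 25% | 5.5% to 57.2% |
| By dose level, three merged | 3/18 = 16.7% | 3.6% to 41.4% |

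The intervals are wide and overlap, as expected with 6 per cohort, so even the by-regimen view is only descriptive. The merged rows, however, do not show that the events came from one regimen.

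**Consistency with the PK summaries.** Section 11.1.3 summarises Part 3 plasma concentrations by dose regimen at each sampling day, and Table 3.j schedules plasma samples on Day 14. Rechallenge concentrations would therefore be shown by regimen and rechallenge safety by dose level.

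**Washout wording.** Section 11.1.4 says only that the dose follows washout. Sections 11.1.4.1 to 11.1.4.4 add the 7 days. Table 3.f footnote b, Table 3.j footnote a and Section 6.1.4 allow another duration. If the option is used, those four subsections no longer describe the data.

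**The case against.** The strongest defence is that the general rule in Section 11.1.4 already covers all Part 3 safety data by dose regimen, and that Table 6.a names the Part 3 regimen as titration, washout and redosing together. Day 14 data could then also enter the by-regimen tables, with the dose-level rechallenge tables as an extra cut. The text neither says nor excludes this. Even if it is right, it yields no rechallenge-specific summary by regimen. By-subject listings keep the data separable, but a listing is not a planned summary. A statistical analysis plan could add columns, but here the protocol states the grouping itself.

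It is also fair to say that the secondary objective names no contrast between regimens, and that grouping by the dose given fits its wording. That stands, but the rationale in Section 6.3.2.5 does link the redosing to attenuation gained through titration.

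Several stronger readings are tempting and are not supported:

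- A reader might infer that washout length is a factor the rechallenge is designed to test. The protocol plans 168 hours and makes the duration adaptable. It is not a designed comparison.
- A reader might infer that the merging is certain. It needs at least two cohorts to be run at one maximum dose, and Cohort 20 may go higher. Different washouts add to it only if the option is used.
- A reader might infer that columns would be falsely headed as 7 days. The group names carry no number; the figure stands only in the introductory wording of four subsections.
- A reader might add the ±1 day window around Day 14. It applies to every Part 3 cohort alike, and regrouping would not remove it.

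**Conclusion.** The point holds in a limited form. The protocol fixes a rechallenge grouping with no regimen level, unlike its own main Part 3 safety tables. Where cohorts share a maximum dose, which Section 6.1.4 allows and for Cohorts 18 and 19 suggests, 12 or 18 active subjects with different titration histories form one column. The rechallenge column then has no counterpart in the by-regimen pre-washout tables, and loss of attenuation cannot be judged regimen by regimen from the planned summaries.

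This rests on the shared maximum dose; different washouts would aggravate it but are not needed. The 50%, 25% and 17% figures rest on assumed counts and show only the kind of masking that can occur. The 7-day wording is a separate, smaller inconsistency between sections. The change is worth making because it bears on a stated secondary objective and costs little in a descriptive study.

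**What to change.** In Sections 1.0 and 11.1.4 to 11.1.4.4, present the rechallenge safety summaries by Part 3 dose regimen, and separate groups whose planned washout differed. Keep single dose level and overall as secondary, pooled columns; there is no need to restrict what the overall column may show. Placebo can stay pooled across cohorts, as now.

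Reconcile the 7-day wording in Sections 11.1.4.1 to 11.1.4.4 with Table 3.f footnote b, Table 3.j footnote a and Section 6.1.4. One way is to refer simply to the dose after washout, as Section 11.1.4 does, and to report the actual interval since the last dose for each group.

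The cost is a text change and at most three active columns. The downside is 6 active subjects per column, which is the size each cohort was given.
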